3. OVERALL STUDY DESIGN

3.1. Study Design

[figure not shown]
This is a Phase 3, randomized, double-blind, placebo-controlled study to explore the effect of oral ozanimod as an induction treatment for subjects with moderately to severely active CD, defined as a CDAI score ≥ 220 to ≤ 450 . Approximately 600 subjects with active clinical symptoms and mucosal inflammation will be randomized in a 2:1 ratio to receive either ozanimod 0.92 mg or placebo. Subjects will be stratified [REDACTED]. A maximum of approximately 50% of subjects with a history of treatment with marketed biologic agents (eg, TNF antagonists, anti-IL-12/23, and anti-integrin therapy) will be recruited. This limit will ensure the enrollment of subjects who have failed or been intolerant to corticosteroids or immunomodulators but never failed a biologic agent.

The primary endpoint of the study is the proportion of subjects in clinical remission (CDAI score < 150) at Week 12. Key secondary endpoints are provided in Section 2. A futility analysis will be conducted when approximately 300 subjects have been enrolled, with a similar proportion of biological naïve to biological exposed population as that in the overall study population. [REDACTED]

[REDACTED] Subjects who received placebo and are in clinical response, clinical remission, and/or have an average daily stool frequency score ≤ 3 and an average abdominal pain score ≤ 1 with abdominal pain and stool frequency no worse than baseline at the end of this study will continue to receive placebo in a blinded fashion in the Maintenance Study. Those subjects not meeting the criteria outlined above at the end of the Induction Study will be eligible to enter the OLE Study (RPC01-3204). Subjects receiving any medical or surgical intervention for the treatment of CD that meet the criteria for treatment failure (Section 9.8) will be discontinued from the study and will not be eligible for the Maintenance or OLE Studies.

The study will be conducted in compliance with International Council on Harmonisation (ICH) of Technical Requirements for Registration of Pharmaceuticals for Human Use/Good Clinical Practice (GCP) and applicable regulatory requirements.

Figure 1: Overall Study Design

Abbreviations: OLE = Open-Label Extension.

3.2. Study Duration for Subjects

Subjects who complete the Induction Study are anticipated to receive 12 weeks of treatment (12-week Induction Study). Subjects not entering the Maintenance Study or Open-Label Extension Study will have [REDACTED]

3.3. End of Study

The end of study (Induction Study RPC01-3202) is defined as either the date of the last visit of the last subject to complete the [REDACTED] date of receipt of the last data point from the last subject that is required for primary or secondary analysis, as pre-specified in the protocol, whichever is the later date.

4. STUDY POPULATION

4.1. Number of Subjects

Approximately 600 subjects with moderately to severely active CD will be randomized in a 2:1 ratio to receive either ozanimod 0.92 mg or placebo.

4.2. Inclusion Criteria

Subjects must satisfy the following criteria to be enrolled in the study:

1. Male or female subjects aged 18 to 75 years (at Screening)
2. Subject should not have any constraints under local regulations, must provide written informed consent prior to any study-related procedures, and must have the ability to comply with the Table of Events.
3. Subject has signs and symptoms consistent with a diagnosis of CD for at least 3 months (prior to first IP administration). The diagnosis should be confirmed by clinical and endoscopic evidence and corroborated by a histology report. (Note: endoscopy and local histopathology confirmation may be obtained during Screening if no prior report is readily available).
4. Subject has met each of the following 2 criteria:
 - a CDAI score ≥ 220 and ≤ 450
 - an average daily stool frequency ≥ 4 points and/or an abdominal pain of ≥ 2 points
5. Subject has a SES-CD score of ≥ 6 (or SES-CD ≥ 4 in subjects with isolated ileal disease).
6. Subject has an inadequate response or loss of response to or is intolerant of at least 1 of the following systemic CD treatments (see [Appendix B](#) for additional details):
 - corticosteroids
 - immunomodulators
 - biologic therapies (eg, ustekinumab, TNF α antagonists, or vedolizumab)
7. If the subject is taking the following background therapies for CD, a stable dose must be maintained throughout the study beginning from the screening period as indicated below:
 - oral aminosalicylates (eg, mesalamine, sulfasalazine, olsalazine, balsalazide) with a stable dose for at least [REDACTED] prior to Screening endoscopy
 - prednisone (doses [REDACTED]) or equivalent with a stable dose for at least [REDACTED] prior to Screening endoscopy
 - budesonide therapy (doses [REDACTED]) or beclomethasone (doses [REDACTED]) at a stable dose for at least [REDACTED] prior to the Screening endoscopy
8. Subject at high risk (ie, family history, CD duration) for colonic malignancy has documented evidence of having had a surveillance colonoscopy within the last 2 years or according to local and national medical guidelines to evaluate for polyps, dysplasia, or

malignancy. If there is no recent history of surveillance colonoscopy, this can be done as part of the colonoscopy performed during Screening. Any visualized adenomatous polyps must be removed and any suspicious lesion confirmed free of cancer and/or dysplasia prior to randomization.

9. Female subjects of childbearing potential (FCBP):

Note: For the purposes of this study, a female subject is considered to be of childbearing potential if 1) has not undergone a hysterectomy (the surgical removal of the uterus) or bilateral oophorectomy (the surgical removal of both ovaries) or 2) has not been postmenopausal for at least 24 consecutive months (that is, has had menses at any time during the preceding 24 consecutive months). Must agree to practice a highly effective method of contraception throughout the study until completion of the [REDACTED]. Highly effective methods of contraception are those that alone or in combination result in a failure rate of a Pearl Index of less than 1% per year when used consistently and correctly. Examples of acceptable methods of birth control in the study are the following:

- combined hormonal (containing oestrogen and progestogen) contraception, which may be oral, intravaginal, or transdermal
- progestogen-only hormonal contraception associated with inhibition of ovulation, which may be oral, injectable, or implantable
- placement of an intrauterine device (IUD)
- placement of an intrauterine hormone-releasing system (IUS)
- bilateral tubal occlusion
- vasectomized partner
- complete sexual abstinence

Periodic abstinence (calendar, symptothermal, post-ovulation methods), withdrawal (coitus interruptus), spermicides only, and lactational amenorrhoea method are not acceptable methods of contraception.

Counseling about pregnancy precautions and the potential risks of fetal exposure must be conducted for FCBP. The Investigator will educate all FCBP about the different options of contraceptive methods or abstinence at Screening and Day 1, as appropriate. The subject will be re-educated every time her contraceptive measures/methods or ability to become pregnant changes. The female subject's chosen form of contraception must be effective by the time the female subject is randomized into the study (for example, hormonal contraception should be initiated at least 28 days before randomization).

10. Subject must have documentation of positive varicella zoster virus (VZV) [REDACTED] or complete VZV vaccination at least 30 days prior to randomization. See Section 11.3.

4.3. Exclusion Criteria

The presence of any of the following will exclude a subject from enrollment or at the timepoint specified in the following criteria:

Exclusions Related to General Health:

1. Subject has any clinically relevant cardiovascular, hepatic, neurological, pulmonary [severe respiratory disease (pulmonary fibrosis or chronic obstructive pulmonary disease)], ophthalmological, endocrine, psychiatric, or other major systemic disease making implementation of the protocol or interpretation of the study difficult or that would put the subject at risk by participating in the study.
2. Subject is likely to require, in the physician's judgment, bowel resection within 12 weeks of entry into the study.
3. Subject has a diagnosis of UC, indeterminate colitis, radiation colitis, or ischemic colitis, or has strictures with prestenotic dilatation, requiring procedural intervention, or with obstructive symptoms. In addition, subjects with colonic or ileal strictures that are not passable with an age-appropriate colonoscope that the endoscopist normally uses in clinical practice, or strictures in the ileum or ileocecal valve that are fibrotic in nature, will be excluded. Any other modality used in addition to the colonoscopy to assess this criterion must be discussed with the Medical Monitor.
4. Subject has current stoma, ileal-anal pouch anastomosis, fistula that is likely to require, in the physician's judgment, surgical or medical intervention within 12 weeks of entry into the study or need for ileostomy or colostomy.
5. Subject has extensive small bowel resection (> 100 cm) or known diagnosis of short bowel syndrome, or subject requires total parenteral nutrition.
6. Subject has suspected or diagnosed intra-abdominal or perianal abscess that has not been appropriately treated.
7. Subject has documentation of positive test for toxin producing *Clostridium difficile* (*C. difficile*), or polymerase chain reaction (PCR) examination of the stool. If positive, subjects may be rescreened after appropriate treatment and retested no earlier than 7 days after completion of treatment.
8. Subject has documentation of positive examination for pathogens (ova and parasites, and bacteria). If positive, subjects may be treated and rescreened.
9. Subject is pregnant, lactating, or has a positive serum beta human chorionic gonadotropin (β -hCG) test measured during Screening.
10. Subject has any condition that would make implementation of the protocol or interpretation of the study difficult or that would put the subject at risk by participating in the study, including history or presence of the following clinically relevant cardiovascular conditions:
 - Recent (within the last 6 months) occurrence of myocardial infarction, unstable angina, stroke, transient ischemic attack, symptomatic bradycardia, decompensated

- heart failure requiring hospitalization, Class III/IV heart failure, or severe untreated sleep apnea
- Second degree (Mobitz type II) atrioventricular (AV) block, third degree AV block, sick sinus syndrome or sino-atrial block in subjects without a pacemaker in place (for subjects with a pacemaker in place, [REDACTED]); if second degree Type II or third degree AV block is due to concomitant medication, consult Medical Monitor prior to Screening
 - Prolonged QT interval corrected for heart rate using Fridericia's formula (QTcF) (QTcF > 450 msec males, > 470 msec females) at either Screening or Day 1 Predose assessment.
 - Resting [REDACTED] when taking vitals as part of the physical examination at either Screening or Day 1 Predose assessment. One recheck is allowed for subjects with [REDACTED] per visit (ie, during the Screening and/or Day 1 Predose assessment visit).

[figure not shown]
Note: Subjects with certain preexisting cardiac conditions, as detailed [REDACTED], may be considered for participation in the trial.

11. Subject has a history of diabetes mellitus type 1, or uncontrolled diabetes mellitus type 2 with hemoglobin A1c (HbA1c) > 9% or is a diabetic subject with significant comorbid conditions such as retinopathy or nephropathy.
12. Subject has a history of uveitis (within the last year prior to Screening) or a history of macular edema.
13. Subject has a known active bacterial, viral, fungal (excluding fungal infection of nail beds, minor upper respiratory tract infections, and minor skin infections), mycobacterial infection (including tuberculosis [TB] or atypical mycobacterial disease) or any major episode of infection that either required hospitalization, treatment with intravenous (IV) antibiotics within 30 days of Screening, or treatment with oral antibiotics within 14 days of Screening
 - Note: In the case of a known SARS-CoV-2 infection, symptoms must have completely resolved and based on Investigator assessment in consultation with the Clinical Trial Physician / Medical Monitor, there are no sequelae that would place the subject at a higher risk of receiving investigational treatment. [REDACTED]
[REDACTED] See [Appendix C](#) for more details.
14. History or known presence of recurrent or chronic infection (eg, hepatitis B virus (HBV), hepatitis C virus (HCV), human immunodeficiency virus (HIV); recurrent urinary tract infections are allowed.
15. Subject has a history of cancer within 5 years, including solid tumors and hematological malignancies (except basal cell and in situ squamous cell carcinomas of the skin or cervical dysplasia/cancer that have been excised and resolved); or colonic dysplasia that has not been completely removed.

16. Subject has a history of alcohol or drug abuse within 1 year prior to initiation of Screening.

Exclusions Related to Medications:

17. Hypersensitivity to active ingredients or excipients of ozanimod or placebo
18. Prior participation in an ozanimod clinical study.
19. Subject has a history of primary nonresponse to 2 or more approved biologic agents or has been treated with 4 or more biologics for CD. Subjects who have received biologic therapy at sub-therapeutic doses, or durations, should be discussed with the Medical Monitor to assess eligibility.
20. Subject has been treated with a biologic agent within 8 weeks or 5 elimination half-lives (whichever is shorter) prior to the first dose of IP.
21. Subject has a history of treatment with an investigational agent within 5 elimination half-lives of that agent prior to the first dose of IP.

Exclusions Related to Laboratory Results and Other Assessments:

Note: Approval from the Medical Monitor or designee must be obtained if retest is required to be repeated > 2 times for assessing the following criteria:

36. Subject has screening ECG results showing any clinically significant abnormality.
37. Subject has serum creatinine results > 1.4 mg/dL (128 µmol/L) for female or > 1.6 mg/dL (145 µmol/L) for male.
38. Subject has liver function impairment or persisting elevations of aspartate aminotransferase (AST) or alanine aminotransferase (ALT) results > 2 x the upper limit of normal (ULN), or direct bilirubin > 1.5 x ULN.
39. Subject has a platelet count < 100,000/µL (100 GI/L).
40. Subject has hemoglobin < 7.5 g/dL (75 g/L).
41. Subject has neutrophils < 1500/µL (1.5 GI/L).
42. Subject has an absolute white blood cell (WBC) count < 3500/µL (3.5 GI/L).
43. Subject has an absolute lymphocyte count (ALC) < 800 cells/µL (0.80 GI/L).
44. Subject has a forced expiratory volume at 1 second (FEV1) or forced vital capacity (FVC) < 70% of predicted values at screening.

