11. CLINICAL LABORATORY EVALUATIONS

The central laboratory will analyze clinical laboratory samples. Further details of the procedures to be followed for sample collection, storage, and shipment will be documented in a laboratory manual.

[figure not shown]
Repeat testing for protocol-required laboratory tests are to be analyzed by the central laboratory. Additional testing may be performed for significant variations in protocol-required tests at the discretion of the Investigator and the Medical Monitor or designee must be informed. Approval from the Medical Monitor or designee must be obtained if retest is required to be repeated > 2 times and is not already pre-specified in the protocol.

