11.2. Chemistry

- Full chemistry panel at Screening: sodium, potassium, chloride, calcium, magnesium, phosphate, blood urea nitrogen, glucose, HbA1c, albumin, alkaline phosphatase, creatinine, ALT, AST, gamma glutamyltransferase (GGT), total bilirubin, conjugated bilirubin, total cholesterol, triglycerides, [REDACTED], and low-density lipoprotein, [REDACTED]
- All other visits: sodium, potassium, chloride, calcium, magnesium, phosphate, blood urea nitrogen, albumin, alkaline phosphatase, creatinine, ALT, AST, GGT, total bilirubin, conjugated bilirubin, [REDACTED]. Total cholesterol, triglycerides, [REDACTED], and low-density lipoprotein will also be included at the Week 12 or early termination (ET) visit. [REDACTED]

- Urinalysis: Leukocytes, specific gravity, bilirubin, blood, glucose, ketones, pH, protein, and urobilinogen
- The central laboratory will analyze routine blood samples. Details regarding collection of samples, shipment of samples, reporting of results, laboratory reference ranges, and alerting abnormal values will be supplied to the site before site initiation in a study laboratory manual. The results of the analysis will be made available to each site by the central laboratory.

- Investigators will be asked to comment on those abnormalities on the respective laboratory result page, including a notation of the clinical significance of each abnormal finding in the subject's source documents. The laboratory sheets will be filed with the subject's source documents.
- Pregnancy test: Serum β -hCG must be performed at screening in FCBP; urine β -hCG will be performed monthly in FCBP potential at each subsequent visit up until the [REDACTED], and if positive, the subject's dose should be held, and pregnancy status should be confirmed with a serum pregnancy test, including after the [REDACTED], if needed.

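### Do the mg/dL and µmol/L figures in the creatinine exclusion set different eligibility limits?

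*Combined protocol and SAP*

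**What the plan says.** Criterion 37 in protocol Section 4.3 gives each sex a limit in mg/dL with a µmol/L figure in parentheses. For women: "Subject has serum creatinine results > 1.4 mg/dL (128" µmol/L). For men, continuing the same line: "for female or > 1.6 mg/dL (145" µmol/L). The criterion does not say which unit governs or to how many decimals a result is read.

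On measurement, Section 11 says "The central laboratory will analyze clinical laboratory samples", and it sends repeats of protocol-required tests to the same laboratory. On reporting, Section 11.2 refers to a study laboratory manual: "Details regarding collection of samples, shipment of samples, reporting of results, laboratory reference ranges, and alerting abnormal values will be supplied to the site". That manual is not among the documents reviewed.

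The other laboratory exclusions in the list that carry two units (platelets, hemoglobin, neutrophils, white cells, lymphocytes) agree exactly, for example "Subject has hemoglobin < 7.5 g/dL (75 g/L").

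**The concern.** A figure in parentheses after a limit is normally read as the same limit in another unit. Here it is not an exact restatement, and for both sexes the µmol/L figure is the higher one. The two lines also seem to use different conversion factors, about 91.4 for women and 90.6 for men, which suggests that at least one was miscalculated.

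This is a numeric eligibility rule in a multicenter trial. Section 14.2 requires the enrollment criteria to be followed explicitly, and Section 18.1 has monitors verify adherence to them. If the limits really differ, a woman at 1.42 mg/dL (1.42 × 88.4 = 125.5 µmol/L) exceeds one and not the other, and her enrollment could be queried as a deviation. At stake would be consistent screening in a narrow band of values.

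**Working it through.** **Inputs.** From criterion 37: 1.4 mg/dL with 128 µmol/L (women) and 1.6 mg/dL with 145 µmol/L (men). The conversion factor is not in the documents. It follows from the molar mass of creatinine (C4H7N3O, 113.12 g/mol): 10,000 / 113.12 = 88.4 µmol/L per mg/dL.

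**Step 1: exact conversion.** This does not reproduce the plan's figures.

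| | mg/dL limit × 88.4 | stated µmol/L | gap | stated µmol/L ÷ 88.4 |
|---|---|---|---|---|
| Women | 1.4 × 88.4 = 123.8 | 128 | 4.2 (3.4%) | 1.448 mg/dL |
| Men | 1.6 × 88.4 = 141.4 | 145 | 3.6 (2.5%) | 1.640 mg/dL |

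**Step 2: do the two lines contradict each other?** If only the µmol/L figures are allowed to be rounded, the implied factors are 127.5/1.4 to 128.5/1.4 = 91.07 to 91.79 (women) and 144.5/1.6 to 145.5/1.6 = 90.31 to 90.94 (men). These ranges do not overlap. But the mg/dL figures are also printed to limited precision, one decimal. Letting both sides round:

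- women: 127.5/1.45 to 128.5/1.35 = 87.9 to 95.2
- men: 144.5/1.65 to 145.5/1.55 = 87.6 to 93.9

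These ranges overlap widely and both contain 88.4. The document does not show on its own that either line is wrong.

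**Step 3: where do 128 and 145 come from?** With mg/dL shown to one decimal, a result displays as 1.4 up to 1.45 × 88.4 = 128.2 µmol/L, and as 1.6 up to 1.65 × 88.4 = 145.9 µmol/L. The whole numbers on either side of the limits are:

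| µmol/L | mg/dL | shown to one decimal |
|---|---|---|
| 128 | 1.448 | 1.4 |
| 129 | 1.459 | 1.5 |
| 145 | 1.640 | 1.6 |
| 146 | 1.652 | 1.7 |

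So 128 and 145 are the largest whole µmol/L values that display as 1.4 and 1.6. Above 1.4 and above 128 pick out the same whole-number results, and so do above 1.6 and above 145. If each unit is rounded separately from the same underlying value, the classifications differ only between about 128.2 and 128.5 µmol/L for women and between about 145.5 and 145.9 for men. Each sliver is under 0.4 µmol/L wide.

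**Step 4: when would the limits differ?** With mg/dL read to two or more decimals, women from above 1.40 to about 1.45 mg/dL (123.8 to 128 µmol/L) and men from above 1.60 to about 1.64 mg/dL (141.4 to 145 µmol/L) are excluded on mg/dL but not on µmol/L. For that to affect a patient across sites, different sites would also have to apply different units.

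**Step 5: would exact conversion help?** Replacing the µmol/L figures by 124 and 141 while mg/dL is reported to one decimal would create a disagreement. Results of 125 to 128 display as 1.4, and results of 142 to 145 display as 1.6, so these patients would be eligible on mg/dL and excluded on µmol/L.

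**Step 6: the comparison with the other limits.** Platelets, hemoglobin, neutrophils, white cells and lymphocytes convert by powers of ten (7.5 g/dL × 10 = 75 g/L, for instance), so they agree exactly whatever the rounding. Among these laboratory limits, creatinine alone needs a factor that is not a power of ten, so the contrast says nothing about an error.

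**The case for a change.** The best case for a change is that the rounding explanation rests on something the protocol does not say. Criterion 37 names neither a governing unit nor a precision, and the manual that holds the reporting details cannot be seen here. A central laboratory removes differences between assays, but it does not by itself settle what unit or how many decimals appear on each site's report. One added line would remove the doubt, and a monitor facing a result of 1.42 mg/dL would have a written answer.

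Part of this stands: the unit and precision are not in the protocol, and the pairs are not exact conversions. What does not stand is the step from there to inconsistent classification. It needs two facts that the documents do not supply, finer mg/dL reporting and mixed units across sites. Both are matters of laboratory reporting, and Section 11.2 already places the reporting of results and the alerting of abnormal values with the laboratory manual. The pairing itself fits one-decimal reporting closely for both sexes.

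**Conclusion.** No change to the plan is needed. Read as exact values the pairs differ by 4.2 and 3.6 µmol/L. Read as limits on mg/dL results reported to one decimal, they agree for every whole-number µmol/L result. This rests on two assumptions: the conversion factor of 88.4, which is a chemical constant, and one-decimal reporting, which the documents neither state nor contradict.

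If the second assumption fails and sites apply different units, the affected band is about 0.05 mg/dL wide for women and 0.04 for men. The documents give no distribution of screening creatinine, so the number of patients in it cannot be estimated. Even then no result changes. The limit applies before randomization, so it cannot favor an arm, and under Section 9.2 the primary efficacy population is all randomized and dosed subjects, analyzed as randomized. The primary endpoint, the sample size and the testing procedure do not depend on it.

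What remains is a missing operational detail that the central laboratory's reporting setup fills in practice. Nothing here bears on which creatinine limit is clinically right; that is for the sponsor.
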